11.5 Safety Data Collection for Reporting

Safety data collection forms:

The following safety data collection forms are used in this study:

- (Serious) Adverse Event Report Form
- Pregnancy Report Form (paper form)
- Parent-Child/Foetus AE Report Form (paper form)
- Adverse Event of Special Interest (AESI) Report Form

Reportable events:

The following events are reportable to the Safety Check Desk at CRO within 24 hours of awareness:

- All SAEs (related or unrelated) are to be reported independent of their relationship to the study drug via the eCRF or using back-up paper forms in case of eCRF outage
- AEs of special interest (AESI) are to be reported via the eCRF or using back-up paper forms in case of eCRF outage

CONFIDENTIAL

- Pregnancy or lactation is to be reported by using the paper Pregnancy Report Form.
- All events that occur in a Child/Foetus of a pregnant woman who was exposed to the study drug are to be reported by using the paper Parent-Child/Foetus Report Form

Special situations (see definition) should be reported by using the paper (Serious) Adverse Event Report Form by indicating whether serious or not

Non-serious ADRs are to be reported within 4 calendar days via the eCRF or using the paper (Serious) Adverse Event Report Form in case of eCRF outage.

Procedure for Safety Data Reporting (completion and forwarding):

For any new events that are listed in the section above "Reportable events", the Investigator/HCP will report the event by transmitting the Safety Data Collection Form in English via the eCRF or via paper (as described in the section above) to the Sponsor via CRO Safety Check Desk. The Investigator must respond to any request by CRO for follow-up information, as noted above for initial report. CRO should forward the follow-up information within 24 hours to Global Patient Safety, as noted above for initial reports. The sponsor has to meet strict regulatory timelines associated with expedited safety reporting obligations.

The data entered on the safety data collection forms must be consistent with the information recorded in the eCRF. If some data are missing, the form should be completed with the available data and a follow-up report will be sent as soon as possible. The minimum information to be included in the initial report is the following:

- Investigator name and contact details
- Subject identification (e.g., ID number, gender, age)
- Product (including lot/ batch number)
- Description of SAE/ADR/ fatal case/ Special situation

The report should contain causality and seriousness information (for AEs) and must be signed off by the Investigator.

When AE information is communicated via telephone, a written/EDC report must be sent immediately within 24 hours thereafter by fax or e-mail. In such cases the "clock start" for case reporting to Health Authorities is the date and time of the telephone communication.

Exposure during Pregnancy

All pregnancies with an estimated conception date in the period from the date of informed consent signature (where applicable) until the last post-treatment safety visit, or as defined in the protocol, must be recorded by convention in the AE page/section of the CRF. The same rule applies to pregnancies in female patients and to pregnancies in female partners of male patients. The Investigator must notify the Sponsor in an expedited manner of any pregnancy using the Pregnancy Report Form, which must be transmitted according to the same process as described for SAE reporting. The Sponsor must be notified about any pregnancy independent whether the pregnancy is associated with an AE or not.

Investigators must actively follow up, document, and report to the Sponsor on the outcome of all these pregnancies and deliveries even if the subject is withdrawn from the study. If an abnormal outcome occurs, the respective safety data collection form (Pregnancy Report Form, Parent-Child/Foetus AE Report Form) is to be completed and sent to the Sponsor.

Procedure for Follow-up Information

The Investigator must promptly respond to any request by CRO for follow-up information or questions from the Sponsor or delegate, as noted above for initial report. Such requests will be sent to the Investigator via the CRO Safety Check Desk. SAEs/ADRs/AESIs and special situations occurring during the study must be monitored and followed up by the Investigator until stabilization or until the outcome is known, unless the subject has a fatal outcome or is lost to follow-up.

The Investigator will ensure any necessary additional therapeutic measures and follow-up procedures are recorded and reported via a follow-up report form. For all serious cases/ADRs/fatal cases and special situations and AESIs missing information such as outcome, confounders, and causality is to be provided. Additionally, follow-up information of non-serious adverse drug reactions may be required by the Sponsor for medical assessment. Reasonable attempts to obtain follow-up information must be made and documented.

Reporting of any new information on a previously reported event (follow-up) will follow the procedures and timelines of the original report.

CRO should forward the follow-up information within 24 hours to Global Patient Safety, as noted above for initial reports. The sponsor has to meet strict regulatory timelines associated with expedited safety reporting obligations.

11.6 Regulatory Reporting to the Health Authorities

Expedited reporting of serious AEs and non-serious adverse drug reactions to Health Authorities is performed by the Sponsor by the Global Drug Safety department, according to applicable regulations of participating countries.

In addition, the Investigator will comply with any applicable local pharmacovigilance requirements to report appropriate safety data, to national pharmacovigilance systems (e.g. Yellow Card Scheme in UK), as required by country specific reporting requirements.

12 Plans for Disseminating and Communicating Study Results

12.1 Study Report

The completed study will be summarized in a final report that accurately and completely presents the study objectives, methods, results, limitations of the study, and interpretation of the findings.

### 2 List of Abbreviations and Definition of Terms

AE Adverse Event

ANOVA Analysis of VARIANCE
ARR Annualized Relapse Rate

ATC Anatomical Therapeutic Chemical classification

BOCF Baseline Observation Carried Forward

CI Confidence Interval

(e)CRF (electronic) Case Report Form

CM Concomitant Medication
CSR Clinical Study Report

CUA Cumulative Unique Active

DMD Disease Modifying Drug

DMF Dimethyl fumarate

EDC Electronic Data Capture

EDSS Expanded Disability Status Scale

FAS Full Analysis Set

HRQoL Health-Related Quality of Life

IAP Integrated Analysis Plan
ICF Informed Consent Form

IFN Interferon

IPD Important Protocol Deviations

LOCF Last Observation Carried Forward

MedDRA Medical Dictionary for Regulatory Activities

MRI Magnetic Resonance Imaging

MS Multiple Sclerosis

MSIS-29 Multiple Sclerosis Impact Scale

NR Non-responder
PT Preferred Term
QoL Quality of Life

RRMS Relapsing-remitting Multiple Sclerosis

SAE Serious Adverse Event

Cladribine CLAD CROSS

MS700568 0070 2.0

SAS Statistical Analysis Software

SD Standard Deviation SOC System Organ Class

TEAE Treatment-Emergent Adverse Event

TEAESI Treatment-Emergent Adverse Event of Special Interest

TSQM Treatment Satisfaction Questionnaire for Medication

T25FW Timed 25-Foot Walk

VAS Visual Analogue Scale

WHO-DD World Health Organization Drug Dictionary

9HPT 9-Hole Peg Test

### **Modification History**

Unique Identifier for Version	Date of IAP Version	Author	Changes from the Previous Version
1.0	29 JUN 2020		First version
1.1	25 OCT 2021		Protocol amendment integrated including 2 interim analyses Removal of Screening Log reference and external source data as not feasible to collect. Added list of outputs included in each interim analysis
1.2	11 NOV 2021		Section 9.5 updated adding table describing windowing
2.0	17 NOV 2021		Section 9.5 updated removing windowing for primary and secondary endpoint

## 4 Purpose of the Integrated Analysis Plan

The purpose of this Integrated Analysis Plan (IAP) is to document technical and detailed specifications for the final analyses of data collected for protocol MS700568\_0070. Results of the analyses described in this IAP will be included in the Clinical Study Report (CSR). Additionally, the planned analyses identified in this IAP may be included in regulatory submissions or future manuscripts. Any post-hoc, or unplanned analyses performed to provide results for inclusion in the CSR but not identified in this prospective IAP will be clearly identified in the CSR.

The IAP is prepared in compliance with International Conference on Harmonization (ICH) E9 and describes analyses planned in the study Protocol Section 9.7 (Data Analysis) and any protocol amendment.

## 5 Objectives and Endpoints

Objectives	Endpoints (Outcome Measures)	IAP Section
Primary		
To study the change in annualized relapse rate (ARR) in patients switching from first-line Disease Modifying Drugs (DMDs) to Cladribine tablets, between the 12-month pre-baseline period and over the 12 months period before End of Study follow-up (2 years)	Effectiveness: Difference in ARR between the pre-baseline 12-month period and over the 12 months period before the End of Study follow-up (2 years)	14.1
Secondary		
To assess change in ARR in patients switching from first-line DMDs to Cladribine tablets, between the 12-month pre-baseline period and over the 12 months period after initiation of Cladribine tablets (1 year)	Effectiveness: Difference in ARR between the pre-baseline 12-month period and over the 12 months period after the start of cladribine (1 year)	14.2

and 2)

Objectives	Endpoints (Outcome Measures)	IAP Section
To study effectiveness in 5 subgroups, defined	All effectiveness outcomes for primary	14.1.3
according to the pre-baseline DMD treatment	and secondary objectives will be	14.2.3
(Interferon [IFN]- ß 1a / IFN- ß 1b / Glatiramer	analyzed for the 5 defined subgroups	14.3.3
Acetate, Teriflunomide, Dimethyl fumarate [DMF]).		14.4.3

### **6** Overview of Planned Analyses

Two descriptive interim analyses will be performed, respectively when 30% and 60% of the patients have completed the 12-month follow-up visit, to check if pre-baseline ARR estimate and its variance are consistent with the sample size assumptions. An alpha adjustment for the multiplicity of the analysis will be introduced if the interim analysis will lead to change in sample size strategy. The full list of outputs included in each interim analysis is available in Appendix 18.2.

This study will have a final analysis after database lock. The final analysis will be performed for all patients at the end of study. All final, planned analyses identified in the study protocol and this IAP will be performed only after the last participant has completed the study with all study data in-house, all data queries resolved, and the database is locked. Statistical analyses will be performed on the basis of raw Statistical Analysis Software (SAS) datasets extracted from the electronic Case Report Form (eCRF). These raw data contain as clean as possible eCRF data. The database lock is expected to occur approximately 1 month after Last Patient Last Visit.

A data review meeting will be held prior to the database lock, using a pre-database lock transfer that will also be used for dry-run purpose. In addition, no database can be locked until this IAP has been approved.

## 7 Changes to the Planned Analyses in the Clinical Study Protocol

There are no changes to the analyses planned per protocol.

## 8 Analysis Populations and Subgroups

## 8.1 Definition of Analysis Populations

#### **Full Analysis Set**

The Full Analysis Set (FAS) is defined as all the patients who provided informed consent and who received at least one dose of Cladribine.

## 8.2 Subgroup Definition and Parameterization

Subgroup analyses will be performed on primary and some secondary effectiveness endpoints as defined below. All subgroup analyses will be exploratory, no adjustment for multiplicity will be performed.

For the definition of subgroup level data, data will be taken, as documented in the eCRF. The category "missing" will not be included in any subgroup analysis.

The following subgroups will be defined:

- Pre-baseline most recent Disease Modifying Drug (DMD):
  - Interferon (IFN)- β 1a [IFNβ 1a (Rebif®) 22 µg t.i.w s.c.; IFNβ 1a (Rebif®) 44 µg t.i.w s.c.; IFNβ 1a (Avonex®) 30µg q.w. i.m.; IFNβ 1a (Plegridy®) 94µg q2wk s.c.; IFNβ 1a (Plegridy®) 125µg q2wk s.c.]
  - $\circ$  IFN-  $\beta$  1b [IFN $\beta$  1b (Betaferon®, Extavia®) 250µg every other day]
  - O Glatiramer Acetate [Glatiramer acetate (Copaxone, CLIFT) 20mg q.d. s.c.; Glatiramer acetate (Copaxone, CLIFT) 40mg t.i.w s.c.]
  - o Teriflunomide [Teriflunomide 14mg]
  - o Dimethyl fumarate (DMF) [Dimethyl fumarate 120mg; Dimethyl fumarate 240mg]

## **9** General Specifications for Data Analyses

This section describes any general specifications not included in subsequent sections. This study is a single cohort study and no comparison between groups is planned. The "start date" for this study is the start date of treatment with Cladribine.

Continuous variables will be summarized using descriptive statistics, i.e. the number of patients with non-missing values (n), the number of patients with missing values (nmiss), mean, standard deviation (SD), median, 25th percentile (Q1) and 75th percentile (Q3), minimum, and maximum. If there are no missing values, the number of patients with missing values (nmiss) should be indicated by a 0. Mean, median, Q1, Q3, minimum and maximum will be reported with the same number of decimal places as collected in raw data while SD will be reported with one extra decimal place.

Qualitative variables will be summarized by frequency counts and percentages. Unless otherwise stated the calculation of proportions will be based on the number of patients of the analysis set of interest. Therefore, counts of missing observations will be included in the denominator and presented as a separate category.

The overall significance level is 5% two-sided. Confirmatory statistical tests will be performed on the primary outcome only. All other statistical tests mentioned in this IAP are to be regarded as exploratory. Exploratory statistical tests comparing study treatment groups will be performed two-sided. If confidence intervals (CIs) are to be calculated, these will be two-sided with a confidence probability of 95%, unless otherwise specified in this IAP.

In order to provide overall estimates of treatment effects, data will be pooled across sites. The "site" factor will not be considered in statistical models or for subgroup analyses due to the high number of participating sites in contrast to the anticipated small number of patients treated at each site.

All analyses will be performed using SAS® Software version 9.4 or higher. R version 3.2.2 or higher may be used to create some of the figures in case it provides a better alternative layout.

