# 14.3.1 Secondary Objective: Derivation and analysis of the Secondary Outcome 6-month Disability Progression

#### **Derivations**

Disability progression will be assessed using the Visit 4 data and comparing the results with Visit 3. As per definition, if Visit 4 and Visit 3 dates are not separated by at least 24 weeks, disability progression will be set to missing. Disability progression will be assessed if at least one assessment (EDSS, T25FW or 9HPT) is available. As per definition, disability progression will be derived as "Yes" if at least one of the below cases occur:

- Visit 4 EDSS is ≥1 point greater than Visit 3 EDSS if Visit 3 EDSS is greater than 0;
- Visit 4 EDSS is 1.5 or greater when Visit 3 EDSS is 0;
- 20% increase in the T25FW score (average of the two trials) from Visit 3 to Visit 4;
- 20% increase in the 9HPT score (The two trials for each hand are averaged, converted to the reciprocals of the mean times for each hand and then the two reciprocals are averaged) from Visit 3 to Visit 4.

If none of those cases occurred, disability progression will be set to "No".

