#### **Analysis methods**

No missing data imputation will be performed. The proportion of patients with 6-month disability progression at the end of study will be presented including associated 95% Clopper Pearson exact intervals.

Disability progression at Visit 1, Visit 2 and Visit 3 will also be presented and derived in the same way. A bar plot with disability progression from Visit 1 to Visit 4 will be presented. Additionally, the results for EDSS, 9HPT and T25FW scores will be presented descriptively by Visit, including an absolute and relative change from baseline and to the previous visit.

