## 14.3.2 Sensitivity Analyses of the Secondary Outcome 6-month Disability Progression

Four sensitivity analyses will be performed to assess the robustness of the results of the secondary outcome.

The first sensitivity analysis will be a complete case analysis that will derive disability progression only for cases where it can be determined without reservations, setting all the other cases to missing. This means that if only one or two out of the three assessments are available, disability progression will either be "Yes" if those are sufficient for the assessment or "Missing" if progression criteria are not observed in any of the available assessments. The number of patients included in these analyses will be less than the ones includes in the main analysis.

The second sensitivity analysis will include a Non-responder (NR) missing data imputation. All patients for which disability progression cannot be assessed or is "No" but not all three assessments are available will be set to "Yes".

Both approaches will provide a significant underestimation of the treatment effect due to the anticipated missing data in the optional assessments.

A third sensitivity analysis will be performed using EDSS only for disability assessment derivation.

The fourth sensitivity analysis will replicate the above described third sensitivity analysis but by two subgroups:

- Patients with at least one EDSS score obtained within 3 months following a relapse
- Patients with both EDSS scores obtained more than 3 months following a relapse

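### The SAP contradicts itself on the denominator for 6-month disability progression and improvement; its only explicit rule keeps missing outcomes in and shrinks both percentages

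*SAP*

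**What the plan says.** SAP section 9 sets the general rule: "Unless otherwise stated the calculation of proportions will be based on the number of patients of the analysis set of interest", and so "counts of missing observations will be included in the denominator" and shown as their own category. Intervals, where calculated, "these will be two-sided with a confidence probability of 95"%. Section 14 bases the effectiveness analyses on the Full Analysis Set (FAS), defined in 8.1 as "all the patients who provided informed consent and who received at least one dose of Cladribine".

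Section 14.3.1 then specifies the endpoint: "The proportion of patients with 6-month disability progression at the end of study will be presented including associated 95% Clopper Pearson exact intervals". It rules out imputation and names no denominator. Section 14.4.1 does the same for improvement.

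Missing outcomes arise in at least two ways:
- By rule in 14.3.1: "if Visit 4 and Visit 3 dates are not separated by at least 24 weeks, disability progression will be set to missing". Section 14.4.1 repeats this for improvement.
- By withdrawal: under Protocol 9.2.5, patients who switch to another DMD leave the study. They stay in the FAS, but have no Visit 4 if they leave before it.

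Section 14.3.2 describes a complete-case analysis that moves some patients from No to Missing, and says of it: "The number of patients included in these analyses will be less than the ones includes in the main analysis". It expects this analysis, like the non-responder (NR) analysis, to be less favourable than the main one. For improvement, 14.4.2 expects complete-case to overstate the effect and NR to understate it.

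**The concern.** A programmer who follows the only written rule would divide by the whole FAS. A patient whose outcome was never observed then contributes to the denominator and never to the numerator, so in the percentage and its exact interval that patient acts as a non-event. This sits badly with the no-imputation statement in 14.3.1. It also gives Clopper-Pearson a sample size that includes trials nobody observed.

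A programmer who takes the lead from 14.3.2 and 14.4.2 would divide by patients with an outcome. The two readings give different figures for two named secondary endpoints, and the choice could be made after the amount of missing data is known.

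**Working it through.** The plan states no event rate, missing rate or interval width for these endpoints, so there is no figure to reproduce. The only related number is the planned enrolment of 242 (Protocol 9.5), used below as the FAS size on the assumption that every enrolled patient is dosed.

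**1. Effect of the denominator.** Let N be the FAS, M the number with a missing outcome, Y the number with the event, and m = M/N.

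- Section 9 rule: Y/N = [Y/(N − M)] × (1 − m).
- Non-missing denominator: Y/(N − M).

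With exact Clopper-Pearson limits, N = 242, and assumed event and missing rates:

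| Observed rate, missing | Section 9 denominator | Non-missing denominator |
|---|---|---|
| about 10%, 10% (M = 24) | 22/242 = 9.1% (5.8–13.4) | 22/218 = 10.1% (6.4–14.9) |
| about 10%, 20% (M = 48) | 19/242 = 7.9% (4.8–12.0) | 19/194 = 9.8% (6.0–14.9) |
| about 10%, 40% (M = 97) | 14/242 = 5.8% (3.2–9.5) | 14/145 = 9.7% (5.4–15.7) |
| about 15%, 20% (M = 48) | 29/242 = 12.0% (8.2–16.8) | 29/194 = 14.9% (10.2–20.8) |
| about 20%, 30% (M = 73) | 34/242 = 14.0% (9.9–19.1) | 34/169 = 20.1% (14.4–27.0) |

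**2. Coverage.** If outcomes are missing at random, exact binomial summation gives the coverage of the section 9 interval at 10%, 20%, 30% and 40% missing:
- true rate 10%: 95.3%, 88.2%, 72.4%, 48.5%
- true rate 20%: 88.5%, 65.4%, 29.7%, 6.3%

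The non-missing denominator stays between 95.7% and 96.3% in all eight cases.

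**3. Which denominator do the sensitivity analyses assume?** Split the patients without the event into F (all three tests available, No) and P (one or two available, No), so N = Y + F + P + M. Complete-case moves P to missing. NR sets P and M to Yes for progression and to No for improvement. As an example, take Y = 19, F = 60, P = 115, M = 48 (an assumed split, total 242).

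| Analysis | Section 9 denominator | Non-missing denominator |
|---|---|---|
| Main | 19/242 = 7.9% | 19/194 = 9.8% |
| Complete-case | 19/242 = 7.9% | 19/79 = 24.1% |
| NR, improvement | 19/242 = 7.9% | 19/242 = 7.9% |
| NR, progression | 182/242 = 75.2% | 182/242 = 75.2% |

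Under section 9 the complete-case percentage equals the main one whatever the split. For improvement, NR equals it too. Section 14.3.2 expects complete-case progression to look worse than the main result, and 14.4.2 expects complete-case and NR improvement to err in opposite directions. Both expectations hold in the right-hand column and fail in the left.

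**4. Could missing outcomes be common?** Using the SAP's month of 30.4375 days, Visits 3 and 4 are nominally 6 × 30.4375 = 182.6 days apart, against the 168-day minimum, which leaves 14.6 days of slack. If both visits vary independently and uniformly by ±30 days (an assumption), the share of pairs under 168 days is (60 − 14.625)² / (2 × 60²) = 28.6%. At ±15 days it is (30 − 14.625)² / (2 × 30²) = 13.1%. Withdrawals come on top.

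**The case against.** The strongest defence is that the SAP's authors plainly meant an evaluable-patient denominator. Section 9 presents itself as general specification for what later sections do not cover, and step 3 shows that 14.3.2 and 14.4.2 are coherent only on that reading. This stands as evidence of intent. It does not settle the matter, because 14.3.1 and 14.4.1 never say so and section 9 yields only where something else is stated.

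A reader might go further and infer that the plan counts missing patients as not having progressed, so that the reported figure will be too low and will flatter cladribine. The documents do not support that as a settled fact:
- The denominator is contradictory, not fixed at the FAS.
- Missing patients are to be shown as a separate category, not labelled No. They act as non-events only in the percentage and interval, and a reader given the count can recompute the observed-case percentage (though not the interval without redoing it).
- For improvement, the same arithmetic works against cladribine.
- Nothing in the documents shows that patients who leave or switch DMD progress more often, plausible as that is.

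It is also fair to say that these are secondary, descriptive proportions with no confirmatory test, and that the progression NR analysis already gives an upper bound. That bound is loose, because it also turns partly assessed No patients into Yes. In the example it is 75.2%, whereas setting only the missing to Yes gives (19 + 48)/242 = 27.7%.

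**Conclusion.** The SAP is internally inconsistent on the denominator for both disability endpoints, and its one explicit rule is the one that gives a distorted answer. Followed literally, that rule lowers both percentages by the missing fraction, centres the exact interval on the shrunken value, and leaves the complete-case analysis (and NR for improvement) with nothing to test. For progression the resulting estimate falls below the full-cohort rate unless every missing patient truly had no progression.

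The direction under the section 9 reading is certain whenever at least one outcome is missing and at least one event is observed. The size is not: it is about 1 percentage point at 10% missing and a 10% rate, 3 points at 20% missing and a 15% rate, and 6 points at 30% missing and a 20% rate. Those figures rest on assumed event rates, assumed missing rates and an assumed FAS of 242. The primary relapse-rate analysis is not affected.

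**What to change.** In 14.3.1 and 14.4.1, state that the proportion and its Clopper-Pearson interval use FAS patients with a non-missing outcome at the visit concerned, as an explicit exception to section 9. Apply the same wording to the earlier-visit results and to the interim disability tables in Appendix 18.2. Show the number missing in a separate row, by reason, with withdrawal on DMD switch and the 24-week rule listed separately.

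The cost is a sentence or two in each section before database lock. The interval becomes wider, the progression figure less favourable and the improvement figure more favourable than under the section 9 rule.

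This removes a mechanical bias but not informative drop-out, since patients who leave are then excluded instead of diluting the percentage. For progression, the existing NR analysis should therefore be read alongside the main result as an upper bound.
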